#### 6.3.3. Day 8 (Visit 4)

The following procedures will be completed on Day 8:

- Collect blood and urine samples for safety laboratory tests
- Collect pre-dose blood sample for PK analysis
- Collect pre-dose serum sample for PIIANP assessment
- Collect pre-dose urine sample for CTX-II assessment
- Collect pre-dose serum sample for biospecimen banking (if the subject has consented to provide this optional sample)
- Administer the WOMAC
- Record any changes in concomitant medications

- Conduct targeted physical examination
- Obtain weight
- Obtain pre-dose temperature and seated BP and PR
- Obtain 12-lead ECG
- Collect pre-dose synovial fluid sample for biospecimen banking (if the subject has consented to provide this optional sample)
- Administer KA34 or placebo
- Obtain temperature and seated BP and PR 30 minutes after dosing (+/- 5 minute window)
- Assess adverse events by spontaneous reporting and by asking the subject to respond to a non-leading question such as "How do you feel?"
- Remind the subject about study contraception requirements and confirm highly effective contraception is being used (if applicable)

# 6.3.4. Day 15 (Visit 5)

The following procedures will be completed on Day 15:

- Collect pre-dose blood sample for PK analysis
- Collect pre-dose serum sample for PIIANP assessment
- Collect pre-dose urine sample for CTX-II assessment
- Collect pre-dose serum sample for biospecimen banking (if the subject has consented to provide this optional sample)
- Record any changes in concomitant medications
- Obtain weight
- Obtain temperature and seated BP and PR
- Collect pre-dose synovial fluid sample for biospecimen banking (if the subject has consented to provide this optional sample)
- Administer KA34 or placebo
- Obtain temperature and seated BP and PR 30 minutes after dosing (+/- 5 minute window)
- Assess adverse events by spontaneous reporting and by asking the subject to respond to a non-leading question such as "How do you feel?"
- Remind the subject about study contraception requirements and confirm highly effective contraception is being used (if applicable)
- Subjects may be discharged after at least 2 hours of safety observation following the last procedure

### 6.3.5. Day 22 (Visit 6)

The following procedures will be completed on Day 22:

- Collect pre-dose blood sample for PK analysis
- Collect pre-dose serum sample for PIIANP assessment
- Collect pre-dose urine sample for CTX-II assessment
- Collect pre-dose serum sample for biospecimen banking (if the subject has consented to provide this optional sample)
- Record any changes in concomitant medications
- Obtain weight
- Obtain temperature and seated BP and PR
- Collect pre-dose synovial fluid sample for biospecimen banking (if the subject has consented to provide this optional sample)
- Administer KA34 or placebo
- Collect temperature and seated BP and PR 30 minutes after dosing (+/- 5 minute window)
- Assess adverse events by spontaneous reporting and by asking the subject to respond to a non-leading question such as "How do you feel?"
- Remind the subject about study contraception requirements and confirm highly effective contraception is being used (if applicable)
- Subjects may be discharged after at least 2 hours of safety observation following the last procedure

#### 6.3.6. Day 29 (Visit 7)

The following procedures will be completed on Day 29:

- Administer the WOMAC
- Record any changes in concomitant medications
- Conduct targeted physical examination
- Obtain weight
- Obtain temperature and seated BP and PR
- Obtain12-lead ECG
- Collect blood and urine samples for safety laboratory tests
- Collect blood sample for PK analysis
- Collect serum sample for PIIANP assessment
- Collect serum sample for biospecimen banking (if the subject has consented to provide this optional sample)

- Collect urine sample for CTX-II assessment
- Assess adverse events by spontaneous reporting and by asking the subject to respond to a non-leading question such as "How do you feel?"
- Remind the subject about study contraception requirements and confirm highly effective contraception was used for 7 days after the last IP dose (if applicable)

## 6.3.7. Day 50 (Visit 8)

The following procedures will be completed on Day 50:

- Record any changes in concomitant medications
- Assess adverse events by spontaneous reporting and by asking the subject to respond to a non-leading question such as "How do you feel?"

The Day 50 visit may be conducted via telephone. However, the PI may also ask the subject to return to the site on Day 50 and conduct any additional evaluations or assessments required to protect the well-being of the subject.

# 6.3.8. Day 90 (Visit 9)

The following procedures will be completed on Day 90:

- Administer the WOMAC
- Record any changes in concomitant medications
- Conduct full physical examination
- Obtain weight
- Obtain temperature and seated BP and PR
- Obtain 12-lead ECG
- Collect blood and urine samples for safety laboratory tests
- Collect serum sample for PIIANP assessment
- Collect urine sample for CTX-II assessment
- Obtain MRI according to the procedures outlined in the Imaging Manual
- Assess adverse events by spontaneous reporting and by asking the subject to respond to a non-leading question such as "How do you feel?"
- Procedures in Visit 9 may be completed in 2 days if there is a conflict with MRI scheduling.

#### 6.3.9. Day 180 (Visit 10)

(For the well-being and safety of the subject related to Covid-19, in addition to extending the visit window, certain tasks of the Day 180 visit that do not require on site visit may be

conducted by phone, text message or email. Physical exam can be conducted by telemedicine. Laboratory assessment can be done at laboratories other the clinical sites)

The following procedures will be completed on Day 180:

- Administer the WOMAC
- Record any changes in concomitant medications
- Conduct a full physical examination
- Obtain weight
- Obtain temperature and seated BP and PR
- Obtain 12-lead ECG
- Collect blood and urine samples for safety laboratory tests
- Collect serum sample for PIIANP assessment
- Collect urine sample for CTX-II assessment
- Obtain MRI according to the procedures outlined in the Imaging Manual
- Assess adverse events by spontaneous reporting and by asking the subject to respond to a non-leading question such as "How do you feel?"
- Procedures in Visit 10 may be completed in 2 days if there is a conflict with MRI scheduling.

# 6.4. Subject Withdrawal

Subjects may withdraw from the study at any time at their own request or they may be withdrawn at any time at the discretion of the investigator or the Sponsor for safety reasons or due to the inability to comply with the protocol-required schedule of visits or procedures. Subjects who request to discontinue receipt of study treatment will be discontinued from the study. An early termination visit should be conducted for subjects who receive study drug and then are prematurely withdrawn from the study if at all possible.

The early termination visit will include a physical exam and documentation of weight, vital signs, ECG, and WOMAC score. A review of ongoing AEs, concomitant medications and confirmation of barrier or contraception use for male subjects at least 7 days from the last day of the received dose will be documented. Blood and urine will be collected for safety laboratory tests (hematology, chemistry, and urinalysis), PK, PIIANP, and CTXII analyses.

If a subject decides to withdraw consent, this should be explained in the source documentation. If possible, the investigator should inquire about the reason for withdrawal, request that the subject return for an early termination visit, and follow up with the subject regarding any unresolved AEs for 30 days.

If a subject does not return for a scheduled visit, every effort should be made to contact the subject. The investigator or site staff should attempt to contact the subject at least twice. After 2 attempts, site staff may send a registered letter to the subject. If no response is received, the subject will be considered lost to follow-up. All attempts to contact the subject

and information received during contact attempts must be recorded in the source documentation.

If the subject withdraws from the study and also withdraws consent for disclosure of future information, no further evaluations should be performed and no additional data should be collected. The Sponsor may retain and continue to use any data collected before such withdrawal of consent.

Subjects who are discontinued from or withdraw from the study may be replaced.

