#### 2.2. Primary Endpoints

• Incidence, relatedness, severity, and duration of treatment emergent adverse events (TEAEs)

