#### 5. STUDY TREATMENTS

For this study, the investigational product is KA34 or matching placebo. KA34 or placebo will be administered at the following dose levels to the single dose cohorts:

- 50 µg per IA injection
- 100 μg per IA injection
- 200 µg per IA injection
- 400 μg per IA injection

KA34 or placebo will be administered once a week for 4 weeks at the following dose levels to the multiple dose cohorts:

- 100 μg per IA injection
- 200 μg per IA injection
- 400 μg per IA injection

KA34 will be supplied by the Sponsor in amber glass vials as a sterile solution with a concentration of 200  $\mu$ g per mL. Matching placebo will be provided in identical vials. Each vial will contain 5 mL of KA34 or placebo. The vials will be packaged in boxes for shipment to investigative sites.

The investigational product (IP) labels will include the protocol number, the contents, the lot number, storage conditions, and an investigational use caution statement.

KA34 should not be administered after the use-by date provided by the Sponsor.

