#### 8. ADVERSE EVENT REPORTING

# 8.1. Reporting Requirements and Timeline

Adverse event (AE) information will be collected in this study from the time of first administration of investigation product (Day 1) until 28 calendar days after the last administration of IP (Day 29 for subjects in the single-ascending dose cohorts and Day 180 for subjects in the multiple-ascending dose cohorts). All observed or volunteered treatment emergent adverse events that occur during this timeframe should be recorded in the source documentation and the CRF. If an adverse event is ongoing at the end of the AE collection period, additional follow-up by the investigator may be required until the event or its sequelae resolve or stabilize at a level acceptable to the investigator and the Medical Monitor.

Serious adverse events (SAEs) must be reported to the Medical Monitor within 24 hours of awareness, regardless of whether the event is determined by the investigator to be related to the investigational product under study. If an SAE is fatal or life -threatening, notification to the Medical Monitor must be made immediately, irrespective of the extent of available event information. This time frame also applies to additional follow-up-information on previously reported events. In the rare situation that the investigator does not become immediately aware of the occurrence of an SAE, the investigator must report the event within 24 hours after learning of it and document the time of his/her first awareness of the event. Serious adverse events (SAEs) that the investigator believes have at least a reasonable possibility of being related to investigational product must be reported to the Medical Monitor even if they occur after the active AE collection period.

The investigator may be requested by the Medical Monitor to obtain specific follow-up information for SAEs or other AEs of special interest in an expedited fashion. This information may be more detailed than that recorded on the CRF. In the case of a subject death, a summary of available autopsy findings must be submitted as soon as possible to the Medical Monitor.

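### Multiple-dose subjects who ask to stop injections are taken off the study, so most of their scheduled safety follow-up to Day 180 is lost

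*Protocol*

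**What the plan says.** - **Stopping treatment (Protocol 6.4).** "Subjects who request to discontinue receipt of study treatment will be discontinued from the study". The rule covers any reason and either arm.
- **What follows (6.4).** "An early termination visit should be conducted for subjects who receive study drug and then are prematurely withdrawn from the study if at all possible". That visit covers examination, weight, vital signs, ECG, WOMAC, AE and medication review, safety laboratory tests, PK, PIIANP and CTX-II. It has no MRI. The paragraph on withdrawal of consent adds, where possible, a request to "follow up with the subject regarding any unresolved AEs for 30 days".
- **Replacement (6.4).** "Subjects who are discontinued from or withdraw from the study may be replaced". Neither the arm nor the dose of a replacement is stated.
- **Dosing (Protocol 5).** "KA34 or placebo will be administered once a week for 4 weeks at the following dose levels to the multiple dose cohorts". The schedule puts these on Days 1, 8, 15 and 22.
- **AE collection (8.1).** One sentence gives two end points: "until 28 calendar days after the last administration of IP" and "Day 180 for subjects in the multiple-ascending dose cohorts". Section 8.1 also allows follow-up of events still ongoing when collection ends, and requires reporting of later SAEs thought to be related.
- **Analysis (SAP).** The safety set is everyone dosed (5.2). TEAEs are tabulated as number and percentage of subjects (17.1). Missing safety data are not imputed (7.1). Early-termination results go into the end-of-study summaries (6.6). Disposition (9) shows study completion or discontinuation with reasons, and has no line for stopping injections alone.

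**The concern.** The primary endpoint is the incidence, relatedness, severity and duration of TEAEs. A subject who stops weekly injections because of knee pain or another event is showing a tolerability outcome. Section 6.4 makes that request end follow-up, although declining an injection is not the same as declining to be observed. The loss can therefore depend on tolerability.

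Nothing in the SAP offsets this. A stopper stays in the denominator for the whole period but can contribute new events only while observed, so the unobserved period counts as event-free. In addition, SAP 6.6 places an early-termination result from about Day 8 to Day 22 in the same summary as the last scheduled visit, which is Day 180 in these cohorts.

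**Working it through.** **Plan's own figure.** Cohort sizes sum to 4 + 4 + 8 + 8 + 12 + 12 + 12 = 60, as stated. Each multiple-dose cohort has 9 active and 3 placebo subjects. The documents give no dropout allowance or power calculation to reproduce.

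**Step 1: visits lost.** From the multiple-dose schedule, a subject who leaves during dosing misses:
- AE assessment at Days 29, 50, 90 and 180, plus any remaining dosing-day visits;
- laboratory tests, ECG, examination and WOMAC at Days 29, 90 and 180;
- MRI at Days 90 and 180, and so has no post-baseline WORMS.

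**Step 2: follow-up lost.** Assumption: the early-termination visit falls on the next planned dosing day (Day 8, 15 or 22). Share lost = (180 − last day followed) / 179, since Day 1 to Day 180 spans 179 days.

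| Last dose received | Ends at early-termination visit | 30 days more for unresolved AEs | AE collection to 28 days after last dose |
|---|---|---|---|
| Dose 1 (Day 1) | Day 8: 172/179 = 96% | Day 38: 142/179 = 79% | Day 29: 151/179 = 84% |
| Dose 2 (Day 8) | Day 15: 165/179 = 92% | Day 45: 135/179 = 75% | Day 36: 144/179 = 80% |
| Dose 3 (Day 15) | Day 22: 158/179 = 88% | Day 52: 128/179 = 72% | Day 43: 137/179 = 77% |

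The Day 180 window is ±30 days. The lowest loss over all readings is (150 − 52)/149 = 98/149 = 66%. The highest is (210 − 8)/209 = 202/209 = 97%.

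**Step 3: effect on late TEAE incidence.** The documents give no rates, so these are assumed: 2 stoppers among 9 active subjects, late-TEAE risk 40% in stoppers and 15% in others, no late event seen in stoppers under 6.4, and any replacements active with 15% risk.

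- Without replacement, full follow-up: (2 × 0.40 + 7 × 0.15)/9 = 1.85/9 = 20.6%. Under 6.4: 1.05/9 = 11.7%.
- With 2 replacements, full follow-up: (2 × 0.40 + 9 × 0.15)/11 = 2.15/11 = 19.5%. Under 6.4: 1.35/11 = 12.3%.
- If stoppers carry no excess risk, the true value is 15%, and 6.4 still gives 11.7% without replacement or 12.3% with it.

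The gap is 0.80/9 = 8.9 percentage points without replacement and 0.80/11 = 7.3 with it. Lost follow-up drives the difference; replacement slightly narrows it.

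**Step 4: chance of seeing a late event.** P(at least one) = 1 − (1 − p)^n. For assumed p of 10%, 20% and 30%, nine subjects followed give 0.61, 0.87 and 0.96. Seven give 0.52, 0.79 and 0.92.

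**The case against.** Much of the tolerability outcome is kept. Withdrawal due to an AE is recorded as such (Protocol 8.1.3). TEAEs leading to discontinuation are counted (SAP 17.1), and those ending study medication are listed (17.1.1). A subject who stops because of a TEAE already counts as having at least one. The early-termination visit is broad, and its results enter the end-of-study summaries. A reader might infer that 30 days of contact is all that remains, but 8.1 also allows ongoing events to be followed and requires later related SAEs to be reported. This stands, and it limits the loss to new late events, chiefly non-serious ones, and to scheduled late safety data.

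The 28-day limb of 8.1 could also be the governing rule. After one, two or three doses, AE collection would then end on Day 29, 36 or 43, so only 21 days beyond the early-termination visit would be lost (29 − 8, 36 − 15, 43 − 22). That reading cannot be excluded for a subject who stops. However, the same sentence names Day 180, the schedule places AE assessments there, and 8.1 does not say whether collection continues after discontinuation under 6.4.

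Three stronger readings are not supported:
- That the results will favour KA34. The rule applies to both arms and to any reason for stopping, so the direction depends on who stops.
- That replacement creates the bias. Step 3 shows otherwise.
- That dose escalation is seriously compromised. Those reviews use Day 8 data, so the effect there should be small.

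Finally, this is a descriptive Phase 1 study with no formal safety tests, WOMAC and WORMS are exploratory, and the SAP plans no separate late-TEAE table. This lowers the weight of the point but does not restore the lost data.

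**Conclusion.** The concern holds as a follow-up design weakness. As written, 6.4 ends scheduled observation for a multiple-dose subject who asks to stop injections, and no other section keeps that subject on the later visits. Measured to Day 180, the loss is 66% to 97% on every reading examined. Late TEAE incidence, by term and severity, can be understated, more so in the arm with more stoppers.

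The size of the understatement is unknown. The Step 3 figures rest on assumed numbers of stoppers and assumed risks, and the percentages in Step 2 on the assumed timing of the early-termination visit. That stoppers are those who tolerate KA34 least is a plausible inference, not something the documents state. The change is worth making because it is cheap and bears on the primary endpoint; the documents do not show that the safety conclusions would be invalid without it.

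**What to change.** 1. **Protocol 6.4.** Replace the sentence on requests to stop treatment with: *Subjects who stop study injections will be asked to remain in the study and complete the remaining scheduled visits and assessments without injection.* Leave unchanged the provisions for withdrawal of consent, loss to follow-up, and withdrawal by the investigator or Sponsor. Use the early-termination visit only for those who leave the study. This also reduces the number of Day 8 to Day 22 results summarised with Day 180.
2. **SAP 9.** Report stopped injections and left study as separate lines, each with reasons, and identify replacements in the disposition table.
3. **Protocol 8.1.** Reconcile the two end points for AE collection. 28 days after the last planned dose is Day 22 + 28 = Day 50, not Day 180. State what applies to a subject who stops early.

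The cost is protocol and consent wording and an extra disposition line. Keeping stoppers as well as replacements adds some visits and MRIs. Some stoppers will decline to attend, so the gain is partial. No dose or treatment-stopping rule is changed.

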#### 7. ASSESSMENTS

Every effort should be made to ensure that all protocol-required tests and procedures are completed. However, there may be circumstances outside the control of the investigator that make it impossible to comply with the Schedule of Assessments. In such cases, the investigator should take all steps necessary to ensure the safety and well-being of the subject. When a protocol-required test is not performed, the investigator will document the reason for the missed test and any corrective and preventive actions that he or she has taken in the source documentation. The Sponsor's designated representative should be informed of any protocol deviations that impact subject safety within 24 hours of awareness.

# **7.1. Safety**

# 7.1.1. Laboratory Tests

The following safety laboratory tests will be performed as defined in the Schedule of Activities and Study Procedures section of this protocol at the site local laboratory:

 Table 1
 Laboratory Tests

| Hematology – Complete Blood Count   |   |  |
|---|---|--|
| 
 
Red Blood Cell (RBC) Count
 
Hemoglobin (Hb)
 
Hematocrit (Hct)
 
Mean Corpuscular Volume (MCV)
 
Mean Corpuscular Hemoglobin (MCH)
 
Mean Corpuscular Hemoglobin Concentration (MCHC)
 
Platelet Count (Plt)
 
 | 
 
White Blood Cell (WBC) Count
 
Absolute Neutrophil Count
 
Absolute Lymphocyte Count
 
Absolute Monocyte Count
 
Absolute Eosinophil Count
 
Absolute Basophil Count
 
 |  |
| Chemistry – Metabolic Panel   |   |  |
| 
 
Glucose
 
Calcium
 
Albumin
 
Total Protein
 
Sodium
 
Potassium
 
Bicarbonate (Total CO2)
 
Chloride
 
   | 
 
Blood Urea Nitrogen (BUN)
 
Creatinine
 
Alkaline Phosphatase (ALP)
 
Alanine Aminotransferase (ALT)
 
Aspartate Aminotransferase (AST)
 
Total Bilirubin
 
            |  |
| Urina   | lysis   |  |
| 
 
Specific Gravity
 
pH
 
Protein
 
Glucose
 
Ketones
 
Blood (Hemoglobin)
 
Leukocyte Esterase
 
   | 
 
Nitrite
 
Bilirubin
 
Urobilinogen
 
Microscopic ExaminationA
 
   |  |
| Other Labor   | atory Tests   |  |
| 
 
Follicle-Stimulating Hormone (FSH)B
 
Urine Drug Screen
 
   |   |  |

A Only if urine dipstick is positive for blood, protein, nitrites or leukocyte esterase

B For female subjects

The minimum requirement for urine drug screening includes cocaine, opiates/opioids, benzodiazepines, and amphetamine.

Urine drug screening conducted during Screening in the SAD and MAD part of the study must be negative for subjects to receive investigational product.

Unscheduled clinical laboratory assessments may be obtained at any time during the study to assess potential safety concerns. In any instances where a subject's liver function test results or clinical signs or symptoms suggest that the subject may be experiencing a drug-induced liver injury, the additional tests listed in Table 2 should be conducted and the results should be discussed with the Medical Monitor.

# Table 2 Tests for Suspected Cases of Drug-Induced Liver Injury (DILI)

- ALP
- ALT
- AST
- Total Bilirubin
- Direct Bilirubin
- Indirect Bilirubin
- Albumin
- Creatine Kinase (CK)
- Gamma-Glutamyl Transferase (GGT)
- Prothombin Time and International Normalized Ratio (PT /INR)

The Medical Monitor should be notified of any potential cases of drug-induced liver injury within 24 hours of awareness.

